3.4.3. Sample Size and Power

The **primary outcome** of the study is remission of MetS from baseline to the 12-month visit. We hypothesize that at least 40% of patients in the Intervention Arm, and no more than 15% in the control arm will achieve remission. This hypothesis is supported by the ELM proof-of-concept study and published data on 12- and 24-month MetS remission rates of 9-14% in both control groups' patients.^{93, 95, 106} The proposed study employs clusters within the treatment arm only. To estimate sample size, adjustments were made for the intra-class correlation coefficient (ICC). Using data from the ELM proof-of-concept study, we conservatively estimate the ICC to be

A two-sample, two-sided, z-test for proportions will be used to compare the rate of MetS remission between the two treatment arms with an overall significance level of 0.05.

The sample size chosen is 48 patients (16/arm). Required sample sizes were computed under several plausible scenarios, indicated by our proof-of-concept study and other relevant studies. Power was set at 80%, alpha was 0.05, and a 20% dropout rate was assumed. **Figure 5** shows that if a sample size of 48 is chosen, there will be adequate power to detect a statistical difference between a remission rate as low as 40% in ELM Intervention arm and as high as 15% in the Education Control arm. Similar sample sizes resulted when the number of participating sites, clusters per site, and patients per cluster (between 10 and 13) were varied. There will be inadequate power to detect an effect if the ELM Intervention effect erodes to below a 38% remission and the Education Control remission rate is as high as

15%. However, this state of affairs would suggest that more developmental work on either the treatment or control group is needed before progressing.

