3.4. Statistical analysis

3.4.1. Preliminary considerations

All statistical analyses will be performed using SAS v. 9.2. Basic summary statistics will be calculated for all outcome variables and covariates of interest. Continuous variables will be checked for normality using Q-Q plots.

3.4.1.1. Missing data. Analyses will use an intent-to-treat approach that includes all patients randomized. Study procedures have been proposed to minimize loss of data due to withdrawal or loss. However, sensitivity analyses will be employed to assess the impact of missingness and both conservative and liberal imputations will be used.

3.4.1.2. Adjustment for Clustering. Clusters exist within the intervention arm and analyses thus require consideration of the effects due to clustering, assessed by analyzing within- and between-cluster variance as well as estimating the intraclass correlation coefficient using generalized linear mixed effects modeling. The cluster effect will be deemed significant if the appropriate covariance parameter estimate obtained from the model has p -value <0.05 .¹⁴² In this event, rather than using a two-sample, two-sided, z-test to compare proportions between the two treatment arms and the t-test (or the Mann-Whitney test if distributions are sufficiently non-normal) for the comparison of means, the cluster-adjusted chi-square test will be used to compare proportions and the cluster-adjusted t-test (or the cluster-adjusted Wilcoxon Rank-Sum test if distributions are sufficiently non-normal) will be used to compare means. Similarly, rather than using linear regression analysis to analyze relationships between continuous dependent variables and indicated covariates, linear mixed modeling will be employed. Lastly, rather than using logistic regression analysis to assess relationships between dichotomous dependent variables and indicated covariates, generalized linear mixed effects modeling will be employed.

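### The stated 48 patients at 16 per arm do not add up for two arms, and 48 in total gives about 49% power for 40% versus 15%, not 80%

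*SAP*

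**What the plan says.** All the relevant statements are in SAP section 3.4.3, Sample Size and Power.

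- The size: "The sample size chosen is 48 patients (16/arm" is given as the chosen number.
- The design: the test is a two-sample, two-sided z-test for proportions, used to "compare the rate of MetS remission between the two treatment arms with an overall significance level of 0.05". Section 3.4.2 likewise describes only ELM and a control arm.
- The assumptions: at least 40% remission with ELM, at most 15% in control, and "Power was set at 80%, alpha was 0.05, and a 20% dropout rate was assumed". An adjustment for the intraclass correlation (ICC) is also mentioned, with clusters in the treatment arm only.
- The claim: "if a sample size of 48 is chosen, there will be adequate power to detect a statistical difference" between remission as low as 40% with ELM and as high as 15% in control.
- The lower limit: "There will be inadequate power to detect an effect if the ELM Intervention effect erodes to below a 38% remission" while control remission is as high as 15%. The section adds that this situation would call for further development of the treatment or the control before going on.

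On the analysis set, section 3.4.1 says: "Analyses will use an intent-to-treat approach that includes all patients randomized".

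**The concern.** There are two separate faults. First, the total and the per-arm number contradict each other for a two-arm trial. Second, whichever of them is used, 48 patients in all looks far too few for 80% power at 40% versus 15%.

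The statement concerns the primary outcome. As printed, a reader cannot tell how large the trial is or what power it has. The section also uses its power statement to interpret a disappointing result, as a sign that more development is needed. If 48 is the total, a treatment that truly reaches its 40% target would miss significance about half the time, so a null result would say little about whether development is needed. If 48 is a per-arm or mistyped number, the planned enrolment is misstated.

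**Working it through.** **Inputs, all from SAP section 3.4.3:** p1 = 0.40 (ELM), p2 = 0.15 (control), two-sided alpha 0.05, power 80%, dropout 20%, two arms. Equal allocation is assumed because a single per-arm number is given. Clustering is left out at first, which favours the plan.

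**1. The count.** 2 × 16 = 32, not 48. 48 / 2 = 24, not 16. The number 48 would need three arms of 16, and the SAP describes only two.

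**2. Number needed for the stated power.** With pooled rate (0.40 + 0.15)/2 = 0.275, the pooled z-test formula is

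n per arm = [1.96·√(2 × 0.275 × 0.725) + 0.8416·√(0.40 × 0.60 + 0.15 × 0.85)]² / 0.25²

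= (1.2377 + 0.5102)² / 0.0625 = 48.9, so 49 per arm and 98 in total.

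Allowing for 20% dropout: 49 / 0.8 = 61.25, so 62 per arm and 124 randomised.

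The plan's figure is not reproduced by other versions of the calculation: 47 per arm unpooled, 48 by arcsine, 57 with continuity correction, 39 one-sided. None gives 48 in total or 16 per arm.

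**3. Power at the printed numbers.** Power = Φ[(0.25 − 1.96·s0)/s1], where s0 = √(0.275 × 0.725 × 2/n) and s1 = √((0.24 + 0.1275)/n).

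For n = 24: s0 = 0.1289 and s1 = 0.1237, so power = Φ[(0.25 − 0.2526)/0.1237] = Φ(−0.021) = 0.49.

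| Evaluable per arm | Pooled formula | Exact enumeration of the same test |
|---|---|---|
| 16 | 35% | 38% |
| 19 (24 less 20%) | 40% | 42% |
| 24 | 49% | 51% |
| 38 (48 less 20%) | 69% | 71% |
| 48 | 79% | 80% |
| 49 | 80% | 81% |

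**4. Unequal splits of 48.** Over all splits, the pooled formula peaks at 50% (20 ELM, 28 control). Exact enumeration peaks at 55%. By the pooled formula, 32 ELM and 16 control gives 41%; 16 ELM and 32 control gives 49%.

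**5. A lower control rate.** The section cites "published data on 12- and 24-month MetS remission rates of 9-14" percent. At the most favourable end, 40% versus 9%, 24 per arm gives 72% (75% exact), still short of 80%.

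**6. Detectable rate and the 38% limit.** Against 15% in control, the smallest ELM rate detectable with 80% power is 52% at 24 per arm and 57% at 19 per arm. At 38% versus 15%, power is 44% at 24 per arm and 36% at 19 per arm.

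**7. Clustering.** The ICC value cannot be read in the available text. With a design effect of 1 + (m − 1)·ICC applied to the ELM arm only, m = 10 to 13 as in the section, and an assumed ICC of 0.01 to 0.10, power at 24 per arm falls from about 48% to 38%. An ICC of zero leaves it at 49%.

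**The case against.** The strongest counter-argument is that this is a labelling or typing error and the trial may not be underpowered. If 48 means evaluable patients per arm, power is 79% by the pooled formula and 80% exactly, which matches the target; 60 randomised per arm would leave 60 × 0.8 = 48 after dropout. That is a real possibility. It still contradicts 16 per arm, leaves no room for the ICC adjustment the section says was made, and means the enrolment figure is wrong. The number 48 is also printed twice, the second time in the power claim itself.

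The ICC value and Figure 5 cannot be seen in the available text, and the protocol may carry the right number. Neither absence is held against the plan. An ICC of zero or more can only leave power unchanged or lower it, so the hidden value cannot raise 49% to 80%.

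Three points of detail are fair:

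- The 50% ceiling over all splits belongs to the pooled formula; the exact ceiling is 55%.
- The sentence about 38% does not say that power is inadequate only below that rate. Taken literally it is true at 48 patients, where power at 38% is 44%. What fails is the explicit claim of adequacy at 40% and the implied adequacy from 38% upwards.
- The figures after dropout assume that dropouts leave the analysis, whereas section 3.4.1 keeps everyone randomised. They are illustrations; the main result is the 49% before dropout.

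**Conclusion.** The concern holds. The total and the per-arm number are inconsistent for two arms. With 48 as the total, power at 40% versus 15% is about 49% (51% exact) at 24 per arm, and no split brings it above 50% (55% exact). The stated 80% needs 49 evaluable patients per arm, about twice the 24 that a total of 48 allows.

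These results rest on the section's own rates, test and alpha, with no clustering and no dropout, which is the favourable case. Whether the sample size or the power statement is the misprint cannot be settled from the SAP. Because it concerns the size and power of the primary comparison, it must be corrected.

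**What to change.** Reconcile the total and the per-arm number in section 3.4.3, say whether they count randomised or evaluable patients, and restate power for that number.

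- **If 48 is the true total (24 per arm):** replace the claim of adequate, 80% power with about 49%, lower once the section's ICC is applied. If 20% of patients would be lost from the analysis, the figure is about 40%. Replace the 40% detectable rate with about 52% (57% after that loss). Withdraw the suggestion that power is adequate down to 38%, and the inference about further development that depends on it.
- **If 48 is a per-arm or mistyped number:** print the correct total and per-arm numbers, with power after dropout and after the ICC adjustment.

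The cost is SAP wording only, with no extra patients. If 48 is the true total, the stated power becomes less favourable.

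### At a total of 48 in equal arms, the ELM arm holds one or two groups; the sample-size stability statement fits only a larger trial, and the rule that decides on cluster adjustment from the trial's own data almost never adjusts

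*SAP*

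**What the plan says.** Section 3.4.3 states "The sample size chosen is 48 patients (16/arm)" and describes a comparison of two arms with "A two-sample, two-sided, z-test for proportions will be used". Its inputs are remission of 40% under ELM and 15% under control, and "Power was set at 80%, alpha was 0.05, and a 20% dropout rate was assumed". Clusters exist in the ELM arm only. The planning ICC comes from the ELM proof-of-concept study, not from this trial. The section concludes that "if a sample size of 48 is chosen, there will be adequate power", and adds: "Similar sample sizes resulted when the number of participating sites, clusters per site, and patients per cluster (between 10 and 13) were varied".

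Section 3.4.1.2 (Adjustment for Clustering) has the trial assess the cluster effect itself, by "estimating the intraclass correlation coefficient using generalized linear mixed effects modeling". The cluster-adjusted tests replace the plain z-test and t-test only if the covariance parameter has p below 0.05. Section 3.4.2 applies this rule to the primary 12-month comparison and, under Secondary Aim 2, to the 24-month comparison.

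**The concern.** Two statements depend on how many ELM groups there are, and the plan never gives that number. The first is that the required sample size is stable across sites, clusters per site and cluster size. That needs a design with enough groups to arrange in different ways. The second is that the trial can measure its own cluster effect and choose the primary test from the result. That needs enough groups to estimate a between-group variance.

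If there are only one or two groups, a non-significant cluster variance says nothing about whether clustering is present. The plan would still treat it as permission to ignore clustering, and the false-positive rate of the primary test would exceed the stated 0.05.

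**Working it through.** **Inputs.** From section 3.4.3: total 48, 16 per arm, two arms, 40% vs 15%, two-sided alpha 0.05, power 80%, dropout 20%, clusters of 10 to 13 in ELM only. From section 3.4.1.2: ICC estimated in the trial, adjustment only if p<0.05. Assumed: 1:1 allocation, because a single per-arm figure is given and no ratio is stated. The planning ICC value and Figure 5 are not readable in the copy reviewed, so an ICC of 0.05 is assumed, with 0.02 and 0.10 as a range.

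**1. The plan's own figure.** Pooled z-test, with mean rate 0.275:

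n per arm = [1.960·√(2·0.275·0.725) + 0.8416·√(0.40·0.60 + 0.15·0.85)]² / 0.25² = (1.238 + 0.510)² / 0.0625 = 48.9, so 49.

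After 20% dropout: 49/0.8 = 61.3, so 62 per arm and 124 in all, before any ICC. A total of 48 is not reproduced. The figure 48 fits only as a per-arm number before dropout and ICC (power 79%). Two arms of 16 make 32, not 48.

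**2. Number of ELM groups** = ELM patients divided by group size.

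| ELM patients | Groups at size 13 | Groups at size 10 |
|---|---|---|
| 16 | 1.2 | 1.6 |
| 24 (half of 48) | 1.8 | 2.4 |
| 48 | 3.7 | 4.8 |
| 62 | 4.8 | 6.2 |

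At a total of 48 in equal arms there are one or two groups. Two groups allow only one site with two groups or two sites with one each. A third group needs at least 3 × 10 = 30 ELM patients, 60 in all.

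**3. What the trial can learn about the ICC.** With one group there is no between-group comparison, so the ICC is not identifiable. With two groups of 12 there is 1 between-group degree of freedom. The ANOVA estimate is (F−1)/(F+11). An observed F of 1.6 gives 0.6/12.6 = 0.05, with a normal-theory 95% interval of −0.064 to 0.993. In beta-binomial simulation with a true ICC of 0.05:

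- At a 40% remission rate the estimate is zero or negative in about 58% of trials.
- An F check at p<0.05 fires in about 14% of trials at a 40% rate and about 8% at a 15% rate.
- If the p-value instead comes from a moment estimate divided by its standard error, z cannot exceed about 1/√2 = 0.71 with two groups, so the check never fires.
- At a 40% rate it fires in about 9% of trials for a true ICC of 0.02 and about 20% for 0.10. Five groups raise detection of an ICC of 0.05 only to about 20%.

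**4. Type I error of the primary test** (two ELM groups of 12, 24 controls, 15% in both arms). By hand for the plain test, the ELM variance is inflated by 1 + 11·ICC, so the true variance of the difference is (1 + 11·ICC + 1)/2 times the assumed one:

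- ICC 0.02: ratio 1.11; 1.96/√1.11 = 1.860; two-sided tail 6.3%.
- ICC 0.05: ratio 1.275; 1.96/√1.275 = 1.736; tail 8.3%.
- ICC 0.10: ratio 1.55; 1.96/√1.55 = 1.574; tail 11.5%.

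Simulation agrees. At ICC 0.05 the plain test has about 8.5%. The section 3.4.1.2 switch has about 8%, taking the adjusted test as one that inflates the ELM variance by the estimated ICC. At 0.02 the figure is about 6.5%, and at 0.10 it is 10 to 12%. With the ICC fixed in advance at 0.05 and correct, it is about 4.3%.

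**The case against.** The strongest reply is that the stability sentence concerns required sample sizes across planning scenarios, not the layout of one 48-patient trial. A reader might infer that the stability is impossible, and the SAP does not support that. Between cluster sizes 10 and 13 the design effect at an assumed ICC of 0.05 moves only from 1 + 9·0.05 = 1.45 to 1 + 12·0.05 = 1.60. Required totals after dropout are then 150 to 164, which are indeed similar. The scenarios themselves cannot be checked. What stands is that the sentence is coherent for a trial of about 48 or more per arm and does not fit the total printed beside it.

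A reader might also infer that the ICC cannot be estimated at all. That is literally true for one group only. Two groups give an estimate, but one without usable precision. The sample size does not depend on it, since the planning ICC is external.

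It can also be said that this is a by-product of the contradiction between 48 and 16 per arm. In part it is, but a corrected N does not rescue the switch: 62 per arm gives about five or six groups, and five groups still detect an ICC of 0.05 in only about 20% of trials. Nor does unequal allocation: 32 of 48 in ELM, which the SAP does not state, gives 32/13 = 2.5 to 32/10 = 3.2 groups, and three groups detect it in about 17%.

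Finally, the operating characteristics of a test that always uses the trial's estimated variance do not describe this plan, which adjusts only after a significant check. They are not relied on here.

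**Conclusion.** The point holds in this form. With equal arms and 48 in all, ELM has one or two groups. The stability sentence conflicts with that total and should not be read as a property of the trial as sized. The rule in section 3.4.1.2, followed exactly, leaves the primary and 24-month tests anti-conservative: about 8% type I error at an ICC of 0.05, about 6.5% at 0.02 and 10 to 12% at 0.10.

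The group count rests on 1:1 allocation. The error rates rest on two groups of 12, 24 controls, a beta-binomial outcome and an assumed ICC. The direction does not depend on the exact ICC, provided it is above zero. This should be corrected before analysis.

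**What to change.** 1. Reconcile 48 with 16 per arm. State the total, per-arm n, allocation ratio, planning ICC, and number and size of ELM groups, and recompute the required N from them. Then restate the stability sentence to match, or delete it. The 24 per arm used above is a working assumption and should not be adopted from this note.
2. For the primary and 24-month comparisons, remove both the p<0.05 switch and the trial-estimated ICC. Always inflate the ELM-arm variance with the proof-of-concept ICC already used for planning, fixed in advance, and show the result over a stated range, for example 0 to 0.10.
3. State that with so few groups the trial cannot estimate the ICC with usable precision.

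The wording and one sensitivity table cost little; recomputing N may show that a larger trial is needed. The statistical downside is reliance on an external ICC. Fixing 0.05 gives about 6.6% type I error if the truth is 0.10 and 8.8% if it is 0.15, and is conservative if the truth is smaller. The range makes this visible.
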